# 8.3. Study Device Storage

All clinical trial material must be kept in an appropriate, limited-access, secure location until it is used or returned to the Sponsor or designee for destruction. All study devices must be stored under

the conditions specified on the label, and remain in the original container until it is dispensed. A daily temperature log of the study device storage area must be maintained every working day. Any temperature excursion of study devices should be notified to the Sponsor and the supplies placed in quarantine until further instruction is received from the Sponsor. The study device and unpreserved artificial tears will be delivered to the study centres by the clinical supplies distributor.

The study devices and unpreserved artificial tears must be stored **below 25°C** and must not be frozen. Light exposure must be avoided.

Initially each centre will receive adequate supplies (study devices and unpreserved artificial tears) to cover the study treatment period for a pre-defined number of patients. Additional supplies will be dispatched after taking into account the recruitment rate of each study centre. The investigator or his/her designee will be responsible for correct handling and storage of the study devices and unpreserved artificial tears during the course of the study.

# **8.4.** Administration

The study device will be instilled 4 times daily into both eyes (morning, noon, afternoon and evening).

The study device and the unpreserved artificial tears provided by the Sponsor are to be dispensed only by the investigator or his/her designee, and will be used in accordance with this protocol.

Under no circumstances will the investigator allow the study products to be used other than directed by the protocol. All dispensations and returns of study device have to be documented in the masked pharmacy file provided by the Sponsor (see section 8.5).

In order to ensure patient anonymity, patients will be identified by codes or other means of record identification.

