# 7.8. Randomisation and Masking

The patients who fulfil the inclusion criteria will be randomly assigned (by IWRS/IVRS) in a 1:1 ratio to receive either ALOCROSS® or VISMED® for 12 weeks (84 days) in an investigator-masked fashion.

Each randomised patient will receive numbered study device kits as assigned by the system.

Treatment assignments will be masked to Santen and ITEC employees (except for the Drug Supply personnel), and Investigators. The investigator should try to avoid breaking the masking codes. However, IN CASE OF EMERGENCY ONLY, (i.e. SERIOUS ADVERSE EVENT [SAE]

AND ONLY WHEN THIS INFORMATION INFLUENCES THE MANAGEMENT OF THE PATIENT CARE), the investigator is entitled to unmask the patient by using IWRS, in order to obtain the study device information (i.e. ALOCROSS® or VISMED®) to immediately start the appropriate treatment [to be recorded in the source data and eCRF (electronic Case Report Form)]. The date, time and reason for breaking the code will be recorded. The investigator should inform the Sponsor immediately after unmasking. The details of this unmasking procedure will be described in a separate document. Patients unmasked for the management of a SAE will be discontinued from the study.

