# 8.5. Study Device Accountability and Destruction

The Principal Investigator has overall responsibility for ensuring that an inventory is conducted upon receipt of the clinical supplies. Due to the study being Investigator Masked, all study device accountability and destruction must be undertaken by the Investigator's unmasked designee. The receipt of clinical supplies should be completed, signed and returned as directed by Santen (or designee). A copy must be maintained at the site for the Investigator's records. The Principal Investigator's unmasked designee will keep a current record of the inventory and dispensing of all study devices. This record will be made available to Santen's Un-masked Monitor (or designee) for the purpose of accounting for all clinical supplies. Any discrepancy and/or deficiency must be recorded with an explanation. All supplies sent to investigator must be accounted for and in no case will study device be used in any unauthorised situation.

It is a responsibility of the Principal Investigator to return any unused supplies to the Santen Unmasked monitor (or designee) at the conclusion of the study.

Patients will be instructed to keep all unused, expired or malfunctioning containers (bottle, SDU and box) and will be required to bring unused, expired or malfunctioning study device containers to each clinic visit. The destruction of the unused, expired or malfunctioning containers of study device will be performed according to the instructions of the clinical monitor and has to be documented.

Upon completion or earlier termination of the study the investigator's unmasked designee will, unless otherwise agreed, return to the clinical supplies distributor any surplus quantities, unused containers/bottles/SDU, of study device or unpreserved artificial tears. The investigator's unmasked designee will record each quantity of study device or unpreserved artificial tears that has been damaged or is missing.

Study device supplies will be counted and reconciled at the site before being returned to Santen or designee or being destroyed by the site.

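### Sections 7.8, 8.3, 8.4 and 8.5 conflict on whether the masked investigator may handle study product, leaving the investigator's global rating and the D84 gradings open to avoidable unmasking

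*Protocol*

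**What the plan says.** Section 7.8 sets the mask: "Treatment assignments will be masked to Santen and ITEC employees (except for the Drug Supply personnel), and Investigators". Section 8.5 draws the consequence for product: "Due to the study being Investigator Masked, all study device accountability and destruction must be undertaken by the Investigator's unmasked designee". It adds: "The Principal Investigator's unmasked designee will keep a current record of the inventory and dispensing of all study devices". Section 8.6 gives the compliance check at each visit to the same unmasked role.

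Other provisions are looser. On storage, section 8.3 states: "The investigator or his/her designee will be responsible for correct handling and storage of the study devices and unpreserved artificial tears". Section 8.4 says that the study device and the sponsor's artificial tears "are to be dispensed only by the investigator or his/her designee, and will be used in accordance with this protocol", and that dispensing and returns are documented in a pharmacy file which it calls masked. Section 8.2.3 has whoever dispenses on Day 1 move the detachable box label into the accountability log.

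On returns, section 8.5 first says: "It is a responsibility of the Principal Investigator to return any unused supplies to the Santen Unmasked monitor (or designee"), at study end. Later in the same section the unmasked designee returns surplus and unused product to the clinical supplies distributor. Sections 9.4 and 9.5 list container collection at V4 and V5 without saying who does it; for early discontinuation, 9.5 refers only to an appointed person at the site.

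**The concern.** The protocol itself treats contact with product as a threat to the investigator's mask: that is the reason section 8.5 gives for creating the unmasked role. A permission elsewhere for the investigator to handle and dispense the same product works against that safeguard.

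The mask matters because the design is investigator-masked and several outcomes depend on judgement. These are the staining grades on the modified Oxford scale (10.1) and the investigator's four-category global rating of efficacy (10.6). The overall investigator evaluation at 12 weeks is a named secondary endpoint (5.3.2.1), and the rating is compared between groups at weeks 2, 4 and 12 (12.5.2). If the rater can tell the arms apart, analysis cannot undo the effect.

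**Working it through.** The plan gives no figure on this point, so the check is a comparison of provisions.

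**Step 1. Who is named for each task**

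| Task | Section | Person named |
|---|---|---|
| Accountability, destruction | 8.5 | Unmasked designee only |
| Inventory and dispensing record | 8.5 | Unmasked designee |
| Dispensing and return file | 8.4 | No keeper named; file called masked |
| Compliance check | 8.6 | Unmasked designee |
| Handling, storage | 8.3 | Investigator or designee, masking status not given |
| Dispensing | 8.4 | Investigator or designee, masking status not given |
| Box label into accountability log | 8.2.3 | Whoever dispenses |
| Return of unused supplies (first statement) | 8.5 | Principal Investigator, to the unmasked monitor |
| Return of unused supplies (second statement) | 8.5 | Unmasked designee, to the distributor |
| Container collection, V4 and V5 | 9.4, 9.5 | Nobody named |

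Four mismatches follow. An investigator who dispenses under 8.4 performs, through 8.2.3, an accountability step that 8.5 reserves for the unmasked designee. The file that 8.4 calls masked covers dispensing, whose record 8.5 gives to the unmasked designee. The two return statements differ in actor and in recipient. Among Santen and ITEC employees, 7.8 exempts only Drug Supply personnel, while 8.5 uses an unmasked Santen monitor.

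**Step 2. Can handling reveal anything?** Under 8.2.3, single-dose units carry a blank green sticker for VISMED and a blank white one for ALOCROSS. Under 8.2.2 and 8.2.3, units lie in sealed pouches inside sealed boxes, and the investigational label on pouches and boxes is described as carrying a treatment number and no product name. A sealed kit need not reveal the arm. Opened or returned units can: colour sorts patients into two groups, even for someone who does not know which colour is which product.

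**Step 3. When could it happen?** Section 9 requires assessments in the listed order.
- V2 (9.2): baseline staining is graded before randomisation and dispensing.
- V3 (9.3): no collection or dispensing is listed. The compliance check comes after the staining grade and before the global rating. Section 8.5 has patients bring containers to each visit, but 8.6 gives the compliance check to the unmasked designee.
- V4 (9.4): staining, the primary assessment, comes first; then collection and compliance; then the global rating; then dispensing.
- V5 (9.5): every Day 84 grading follows the V4 collection, and the V5 global rating follows the V5 collection as well.

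Up to the Day 28 staining grade, the permission in 8.4 therefore covers one sealed monthly box, handed over at V2. From the V4 collection onward, a masked investigator who collects containers could see unit stickers before the V4 global rating, the Day 84 gradings and the V5 global rating.

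**Step 4. Whose ratings are affected?** Section 10.6 names the investigator as global rater. Section 10.1 names no grader for staining; that the masked investigator does it is a natural inference from the design, but an inference.

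**Scale.** With 80 patients in approximately 10 centres, 80 / 10 = 8 patients per centre on average, so one centre using the looser route would concern about one tenth of patients.

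**The case against.** The strongest reply is that 8.5 is specific, mandatory and gives its reason, whereas 8.3 and 8.4 are general, allow a designee, and in 8.4 refer the reader on to 8.5. Read as a whole, counting and compliance already belong to the unmasked designee. The Principal Investigator's return duty falls at study end and can be read as oversight, since 8.5 opens by giving that person overall responsibility for the inventory on receipt. Much of this stands. Sections 8.3 and 8.4 permit investigator handling and do not require it, and an investigator who counts units or keeps the dispensing record breaches 8.5.

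The reply does not dispose of the point. An investigator who dispenses follows 8.4 literally and is then told by 8.2.3 to complete the accountability log. Reading the first return sentence as oversight does not explain the different recipient. Nothing in 8.5 or 8.6 says who physically collects containers at V4 and V5, and 7.8 remains inconsistent with the unmasked monitor.

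A reader might infer more than this: that the grader handles returned units before the primary grading, that the mask will fail at some sites without any deviation being recorded, or that false non-inferiority rises by a stated amount. The documents support none of these. The visit order and sealed kits protect most of the period before the Day 28 grade. A type I error figure would need an assumed grading lean and an assumed share of exposed eyes, and the protocol gives neither.

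**Conclusion.** The contradiction is real and lies in the current text of 7.8, 8.3, 8.4 and 8.5, with a gap in 9.4 and 9.5. Its practical reach is modest. It falls mainly on the investigator's global rating at V4 and V5 and on the Day 84 gradings, all secondary; exposure before the primary Day 28 staining grade is limited. The conclusion about bias rests on three conditions: that some sites use the permission in 8.3 and 8.4 or let the investigator collect containers, that sticker colours are visible on the units handled, and, for staining, that the masked investigator is the grader. No numerical effect on the non-inferiority test should be quoted. This is an inexpensive protection against bias that is worth making; it does not show that the primary result is compromised.

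**What to change.** - In 8.3, 8.4, 8.5, 9.4 and 9.5, assign handling, dispensing, container collection and return to the unmasked designee, and state that this person does no efficacy grading or global rating.
- In 8.5, keep one return statement with one actor and one recipient.
- In 8.4, make the pharmacy file an unmasked file closed to graders.
- In 7.8, list the unmasked monitor and the unmasked site designee as exceptions.
- Record any handling of opened or returned units by a grader as a masking deviation.

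The cost is wording: the unmasked designee and monitor already exist in 8.5 and 8.6. The one practical burden is that the unmasked designee must be available at dispensing and collection visits.

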# 8.5. Study Device Accountability and Destruction

The Principal Investigator has overall responsibility for ensuring that an inventory is conducted upon receipt of the clinical supplies. Due to the study being Investigator Masked, all study device accountability and destruction must be undertaken by the Investigator's unmasked designee. The receipt of clinical supplies should be completed, signed and returned as directed by Santen (or designee). A copy must be maintained at the site for the Investigator's records. The Principal Investigator's unmasked designee will keep a current record of the inventory and dispensing of all study devices. This record will be made available to Santen's Un-masked Monitor (or designee) for the purpose of accounting for all clinical supplies. Any discrepancy and/or deficiency must be recorded with an explanation. All supplies sent to investigator must be accounted for and in no case will study device be used in any unauthorised situation.

It is a responsibility of the Principal Investigator to return any unused supplies to the Santen Unmasked monitor (or designee) at the conclusion of the study.

Patients will be instructed to keep all unused, expired or malfunctioning containers (bottle, SDU and box) and will be required to bring unused, expired or malfunctioning study device containers to each clinic visit. The destruction of the unused, expired or malfunctioning containers of study device will be performed according to the instructions of the clinical monitor and has to be documented.

Upon completion or earlier termination of the study the investigator's unmasked designee will, unless otherwise agreed, return to the clinical supplies distributor any surplus quantities, unused containers/bottles/SDU, of study device or unpreserved artificial tears. The investigator's unmasked designee will record each quantity of study device or unpreserved artificial tears that has been damaged or is missing.

Study device supplies will be counted and reconciled at the site before being returned to Santen or designee or being destroyed by the site.

# **8.6.** Treatment Compliance

Patient compliance will be assessed at each visit by the investigator's unmasked designee by questioning the patient and comparing to study device accountability. All reported lack of compliance will be recorded on the eCRF with the reasons. If a patient is persistently non compliant with the study device, the patient should be withdrawn from the study. All patients should be reinstructed about the dosing requirement at each study visit. The authorized unmasked study personnel conducting the re-education must document the process in the patient source records

## 9. SCHEDULE OF OBSERVATIONS AND PROCEDURES

The schedule for all study-related procedures and evaluations is shown in Table 3. Assessments should be completed at the designated visit/time point(s), and should be performed in both eyes.

All assessments should be done in the mentioned order to ensure that additional procedure doesn't interfere with the results of other examinations.

# 9.1. Screening visit (V1): 14 to 7 days before the Baseline visit

- Written informed consent
- Demographic information
- Ocular and systemic medical history
- Previous and concomitant ocular and systemic medications [including artificial tears (AT) usage]
- Verify inclusion and exclusion criteria based on the evaluations just performed:
  - Patients fulfilling the inclusion criteria will discontinue all previous treatments related to dry eye including artificial tears and any prohibited ocular treatments and receive study specific artificial tears for 7 to 14 days
  - o Patients **not fulfilling** the inclusion criteria will be considered as having failed the screening and will not be included in the study
- Filling by the patient of the VAS for the symptoms evaluation of ocular discomfort
- BCDVA
- Slit lamp examination

ALOCROSS® Protocol Version 2
ALHENA study 06 July 2020

- TBUT
- Ocular surface staining score (corneal fluorescein staining and nasal and temporal interpalpebral conjunctival staining (modified Oxford scale))
- Schirmer's test (without anaesthesia)
- IOP
- Dispensation of unpreserved artificial tears (LARMABAK®)
- Patients will be scheduled to return to the site in 7 to 14 days for the Baseline visit.

# 9.2. Baseline visit (V2): Day 1

- Collection of the artificial tears bottle
- Inclusion/exclusion criteria review
- Record of previous and concomitant ocular and systemic medications [other than artificial tear (AT) usage]
- Record adverse events (AEs)
- Filling by the patient of the VAS for the symptoms evaluation of ocular discomfort
- Completion by the patient of the Quality of life questionnaire NEI-VFQ
- BCDVA
- Slit lamp examination
- TBUT
- Ocular surface staining score (corneal fluorescein staining and nasal and temporal interpalpebral conjunctival staining (modified Oxford scale))
- IOP
- Urine pregnancy test (women of childbearing potential only)
- Randomisation in IWRS
- Dispensation of masked study device for a 4-week period according to the randomisation number
- Patients will be scheduled to return to the site in 2 weeks (Day 14 +/-3 days) for the first follow-up visit (V3)

# 9.3. Follow-up visit: Visit 3: Day 14

- Record of concomitant ocular and systemic medications
- Record adverse events (AEs)
- Ocular surface staining score (corneal fluorescein staining and nasal and temporal interpalpebral conjunctival l staining (modified Oxford scale))
- Assessment of compliance to study device

- Global assessment of efficacy by the investigator and the patient
- Patients will be scheduled to return to the site in 2 weeks (Day 28 +/-7 days) for the next study visit (V4)

# 9.4. Follow-up visit: Visit 4: Day 28

- Record of concomitant ocular and systemic medications
- Record adverse events (AEs)
- Filling by the patient of the VAS for the symptoms evaluation of ocular discomfort
- Completion by the patient of the Quality of life questionnaire NEI-VFQ-25
- BCDVA
- Slit lamp examination
- TBUT
- Ocular surface staining score (corneal fluorescein staining and nasal and temporal interpalpebral conjunctival staining (modified Oxford scale))
- Schirmer's test (without anaesthesia)
- IOP
- Urine pregnancy test (women of childbearing potential only)
- Collection of unused, expired or malfunctioning study device containers
- Assessment of compliance to study device
- Global assessment of efficacy by the investigator and the patient
- Dispensation of study device for an 8-week period
- Patients will be scheduled to return to the clinic in 8 weeks (Day 84 +/- 14 days) for the last study visit (V5)

# 9.5. End of treatment visit/End of study visit: Visit 5: Day 84

- Record of concomitant ocular and systemic medications
- Record adverse events (AEs)
- Filling by the patient of the VAS for the symptoms evaluation of ocular discomfort
- Completion by the patient of the Quality of life questionnaire NEI-VFQ-25
- BCDVA
- Slit lamp examination
- TBUT
- Ocular surface staining score (corneal fluorescein staining and nasal and temporal interpalpebral conjunctival staining (modified Oxford scale))

ALOCROSS® Protocol Version 2
ALHENA study 06 July 2020

- Schirmer's test (without anaesthesia)
- IOP
- Urine pregnancy test (women of childbearing potential only)
- Collection of unused, expired or malfunctioning study device containers
- Assessment of compliance to study device
- Global assessment of efficacy by the investigator and the patient

In case of patient's premature study discontinuation:

- the investigator will be asked to perform all the examinations and assessments scheduled for the End of Study Visit
- the investigator will ensure that unused, expired or malfunctioning study devices for the study period has been collected from the patient by the appointed person at the study site

## 10. ASSESSMENT OF EFFICACY

# 10.1. Corneal and Conjunctival Fluorescein Staining

Corneal and conjunctival fluorescein staining will be assessed immediately following the TBUT. Reading will be performed between 1 and 4 minutes after fluorescein instillation for the TBUT, to ensure that the dye does not diffuse into stroma blurring the discrete margin of any staining defects. Both eyes will then be examined at the slit lamp (16X magnification) using a yellow barrier filter and cobalt blue illumination to enhance visibility of staining.

Staining using fluorescein will be graded using the modified Oxford scale (7-point ordinal scale, score 0, 0.5, and 1 to 5 per area [cornea + nasal and temporal conjunctiva]) for cornea and conjunctiva separately, see Appendix A-I Modified Oxford Scale. On this modified scale, the score 0 corresponds to no staining dots and the score 0.5 corresponds to one staining dot per area.

A CFS grade of 0 represents complete corneal clearing.

# **10.2.** Tear Break-Up Time

Tear break-up time (TBUT) will be measured by determining the time to tear break-up. The TBUT will be performed after instillation of 5  $\mu$ L of 2% preservative-free sodium fluorescein solution into the inferior conjunctival cul-de-sac of each eye. To thoroughly mix the fluorescein with the tear film, the patient will be instructed to blink several times. In order to achieve maximum fluorescence, the examiner should wait approximately 30 seconds after instillation before evaluating TBUT. With the aid of a slit lamp at 10X magnification using cobalt blue illumination, the examiner will monitor the integrity of the tear film, noting the time it takes to form lacunae (clear spaces in the tear film) from the time that the eye is opened after the last blink. The TBUT will be measured twice during the first minute after the instillation of the fluorescein. If the 2 readings differ by more than 2 seconds, then a third reading will be taken. The TBUT value will be the average of the 2 or 3 measurements.

